- Unplanned Visit: If the 90-day period between screening and dosing is exceeded due to operational or administrative reasons (eg, enrollment pause due to regulatory or safety review, operational issues causing significant delays), participants will not be screened failed/withdrawn from the study, but will repeat some tests and assessments to re-confirm study/IP administration eligibility criteria, and to rule out significant changes in key tests and assessments (see Sections 5.3 and 5.6).

b. Visit 14 and Visit 19 must be conducted in the course of two (preferably consecutive) days in order to comply with daily blood volume limits. Unless clinical concern and/or participant preference and/or the site's institutional review board's preference warrants in-person visit, the follow-up day visit, on the second day, to complete blood collection, may be performed remotely, to allow blood collection at or close to the participant's home. The following laboratory samples must be collected:

Visit 14 (Week 9)

First day: ELISpot to mini-dystrophin and AAV9, viral vector shedding.

Period	Screening	Baseline	Main Study Period (Year 1)																					Early Discontinuation Visit
			Visit 1 ^a	Visit 2 ^c	Visit 3 ^d	Visit 4	Visit 5	Visit 6	Visit 7	Visit 8 & 9	Visit 10	Visit 11	Visit 12 ^e	Visit 12.2 ^e	Visit 13	Visit 13.1 ^{kk}	Visit 13.2 ^e	Visit 14 ^b	Visit 14.2 ^e	Visit 15 ^e	Visit 16	Visit 17	Visit 18 ^f	Visit 19 ^b
Visit Number/Description	Screening	Baseline	Week 1, Day 1	Week 1, Day 2	Week 1, Day 4	Week 1, Day 6	Week 1, Day 7	Week 2, Day 8 & 9	Week 2, Day 10	Week 2, Day 14	Week 3	Week 4	Week 5	Week 6	Week 7	Week 9	Week 11	Week 13	Week 18	Week 35	Week 47	Week 52		
Visit Day	-90 to -30	-48 to -16	1	2	4	6	7	8 & 9	10	14	21	28	34	42	48	60	74	90	120	240	328	360		
Visit Window (± days)			0	0	0	0	0	0	0	1	1	1	1	3	3	3	3	3	7	7	14	7		

Second day: clinical safety, cardiac troponin I, biomarker (creatinine kinase).

Visit 19 (Week 52)

First day: anti-HAV immunoglobulin M, Hepatitis B surface antigen, Hepatitis C antibody (these tests will not be applicable for Cohort 1 participants confirmed to meet exclusion criterion 15 [see [Section 5.2](#)]), NAb to AAV9, ADA to mini-dystrophin and AAV9, banked biospecimens for biomarkers, viral vector shedding.

Second day: clinical safety, INR, cardiac troponin I, biomarker (creatinine kinase).

c. Visit 2 – Baseline Visit

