- NAb to AAV9, ADA to mini-dystrophin and AAV9, ELISpot to mini-dystrophin and AAV9: Only if the participant discontinues the study before Visit 37 (Year 3, Day 1110).
- Clinical safety: Only if the previous analysis had been done more than 1 month before the date of the Early Discontinuation visit.
- Echocardiogram: Only if the previous echocardiogram had been done more than 6 months before the date of the Early Discontinuation Visit.
- FVC: Only if the previous FVC had been assessed more than 2 months before the date of the Early Discontinuation Visit.
- Viral vector shedding: For any given matrix, if the sample(s) had still been collected at the participant's last study visit, it should also be collected at the Early Discontinuation Visit.

h. **Brief physical and neurological examinations**, as described in [Section 8.2](#), are acceptable post-baseline unless safety concerns warrant full examination.

i. **O2 saturation** will only be measured before the start of the IP infusion and during the inpatient stay post IP administration.

j. **Vital signs** will be measured 3 times per day during the inpatient stay post IP administration.

k. **12-Lead ECG** will be collected and read locally for immediate interpretation and safety monitoring and will be submitted to a central laboratory for standardized interpretation.

l. **Clinical laboratory tests** are described in detail in [Table 3 \(Appendix 2\)](#).

- For urinalysis, a microscopic analysis will be performed only if urine dipstick is positive for blood, protein, nitrites or leukocyte esterase.
- On the following visits: Baseline Visit (Visit 2), Day 60 (Visit 14), Day 120 (Visit 16), Day 240 (Visit 17) and Day 360 (Visit 19), in which functional assessments (eg, NSAA) are performed, blood draws should always be done first, whenever possible, to ensure that the CK levels are obtained prior to the functional test; for additional advice regarding the ordering of assessments please consult the Functional Assessment Manual.

m. **Banked biospecimens for biomarkers** are collected as described in [Section 8.8.4](#).

Period	Screening	Baseline	Main Study Period (Year 1)																				Early Discontinuation Visit ^g
			Visit 1 ^a	Visit 2 ^c	Visit 3 ^d	Visit 4	Visit 5	Visit 6	Visit 7	Visit 8 & 9	Visit 10	Visit 11	Visit 12 ^e	Visit 12.2 ^e	Visit 13	Visit 13.1 ^{kk}	Visit 13.2 ^e	Visit 14 ^b	Visit 14.2 ^e	Visit 15 ^e	Visit 16	Visit 17	Visit 18 ^f

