Visit Number/Description	Screening	Baseline	Week 1, Day 1	Week 1, Day 2	Week 1, Day 4	Week 1, Day 6	Week 1, Day 7	Week 2, Day 8 & 9	Week 2, Day 10	Week 2, Day 14	Week 3	Week 4	Week 5	Week 6	Week 7	Week 9	Week 11	Week 13	Week 18	Week 35	Week 47	Week 52	
Visit Day	-90 to -30	-48 to -16	1	2	4	6	7	8 & 9	10	14	21	28	34	42	48	60	74	90	120	240	328	360	
Visit Window (\pm days)			0	0	0	0	0	0	0	1	1	1	1	3	3	3	3	7	7	14	7		

- n. **Banked biospecimens for genetics** are collected as described in [Section 8.7.2](#).
- o. **Open muscle biopsies** will be obtained in approximately the first 15 participants randomized into Cohorts 1 and 2, and their siblings (with the potential to collect a maximum of 33 if needed), at sites that have been trained and certified by the Sponsor/Sponsor designee to collect open muscle biopsies, following administration of anesthetic (eg, regional block or under general anesthesia) according to institutional standard practice, and only after any imaging and functional assessments scheduled for the same visit have been completed. Baseline Visit muscle biopsies will be performed after randomization. If a muscle biopsy cannot be scheduled on the day of the Baseline Visit, the biopsy may be performed at a later day, as long as it is at least 2 weeks before dosing.
- p. **Echocardiograms** will be collected and read locally for immediate interpretation and safety monitoring and will be submitted to a central laboratory for standardized interpretation.
- q. The **NSAA and CGIS** will be administered by a single clinical evaluator at each visit and whenever possible, the same CE should administer the functional assessments (NSAA, ankle range of motion and FVC) for the same participant throughout the study. The NSAA, ankle range of motion and FVC may be video recorded at the Day 1 (Screening Visit), Baseline Visit (Visit 2), and at the annual visits (ie, Visits 19, 35, 37, 39, 41, 43). If CE re-training is required, the assigned master physiotherapist may request additional visits to be recorded and reviewed. Whenever possible, motor functional assessments should be performed early in the course of the visit, to help reduce the effect of fatigue on the participants' performance; for additional advice regarding the ordering of assessments please consult the Functional Assessment Manual.
- r. **Ambulatory assessment** at Screening (Visit 1) is based only on the ability to perform the 10 m run/walk, as assessed during the NSAA.

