3. OBJECTIVES, ESTIMANDS, AND ENDPOINTS

3.1. Efficacy Objectives, Estimands, and Endpoints

Objectives	Endpoints	Estimands
Primary:	Primary:	Primary:
To demonstrate superior efficacy of treatment with fordadistrogene movaparvovec as compared to placebo based on change from Baseline in the North Star Ambulatory Assessment (NSAA).	Change from Baseline at Week 52 in the NSAA total score.	Primary Estimand: Population: Boys with a genetic diagnosis of DMD who are ambulatory and age ≥ 4 to < 8 years; Variable: Change from Baseline at Week 52 in the NSAA total score; Death or loss of ambulation are identified as potential intercurrent events. Population-level summary: difference in mean changes from Baseline at Week 52 in the NSAA total score between fordadistrogene movaparvovec and placebo.
Secondary:	Secondary:	Secondary:
To quantify the mini-dystrophin expression level in the muscle of participants treated with fordadistrogene movaparvovec.	Change from Baseline in percent normal mini-dystrophin expression level in biceps brachii muscle biopsies at Day 360 using an LCMS assay.	Secondary Estimands: Population: Boys with a genetic diagnosis of DMD who are ambulatory and age ≥ 4 to < 8 years;
To characterize the distribution of mini-dystrophin expression in the muscle of participants treated with fordadistrogene movaparvovec.	Change from Baseline in percent of muscle fibers expressing mini-dystrophin in biceps brachii muscle biopsies at Day 360 as assessed by immunofluorescence.	Variable: Each secondary endpoint;

Objectives	Endpoints	Estimands
To characterize the change in serum creatine kinase (CK) concentration in participants treated with fordadistrogene movaparvovec as compared to placebo.	Change from Baseline at Week 52 in serum CK concentration.	Death or loss of ambulation are identified as potential intercurrent events. Population-level summary: difference in means between fordadistrogene movaparvovec and placebo for each secondary endpoint.
To characterize the skills gained, based on the individual items of the NSAA, in participants treated with fordadistrogene movaparvovec as compared to placebo.	Number of skills gained at Week 52 based on the individual items of the NSAA.	

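### Week 52 CK is drawn on the second day of Visit 19, so it follows the NSAA whenever that day only completes blood collection, although the schedule asks for CK before functional testing

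*Protocol*

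**What the plan says.** All references are to the Protocol.

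- **Endpoint.** Section 3.1 lists as secondary "Change from Baseline at Week 52 in serum CK concentration". Section 9.4.1 analyses it with a repeated-measures model on the log scale, using the visits through Week 52 at which CK is measured. CK is not among the four secondary endpoints in the tested sequence of section 9.1.
- **Two-day visits.** Section 1.3.1, footnote b: "Visit 14 and Visit 19 must be conducted in the course of two (preferably consecutive) days". The reason given is the daily blood volume limit. For Visit 19 the samples are allocated as "Second day: clinical safety, INR, cardiac troponin I, biomarker (creatinine kinase" (the schedule prints creatinine for creatine). CK is also on the second day of Visit 14.
- **Nature of the second day.** Same footnote: "the follow-up day visit, on the second day, to complete blood collection, may be performed remotely", unless clinical concern, or participant or review board preference, calls for attendance.
- **Order of CK and testing.** Footnote l names Baseline and Visits 14, 16, 17 and 19: "blood draws should always be done first, whenever possible, to ensure that the CK levels are obtained prior to the functional test".
- **Timing of motor tests.** Footnote q, whenever possible: "motor functional assessments should be performed early in the course of the visit, to help reduce the effect of fatigue". It names no day.
- **Biopsy.** Footnote o places it "only after any imaging and functional assessments scheduled for the same visit have been completed". Footnote x lets the Visit 19 biopsy move to a later day.

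**The concern.** Footnote l exists because the sponsor wants CK measured before the boy exerts himself in functional testing. Footnote b undoes that at the visit where the endpoint is read. A boy who has the NSAA on day one and a home blood draw on day two gives a post-test CK at Week 52. His Baseline visit is not split, so its CK can be drawn before testing as footnote l asks.

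Two things are at stake. The change from Baseline may then mix a change in resting muscle damage with a response to testing, and possibly to surgery. Sampling conditions may also vary between boys and between visits in the same model. Visits 14 and 19 are split; Baseline and Visits 16 and 17 are not. This adds noise at best. The Visit 19 value has a second use, as the last scheduled CK before Cohort 2 receives the gene therapy.

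**Working it through.** The plan states no figure for this point, so there is nothing to reproduce. The check is a comparison of the footnotes, followed by an illustration with assumed rises.

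**1. Can footnotes b and l both be met?**

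| Second day of Visit 19 | Where the NSAA falls | CK before NSAA? |
|---|---|---|
| Remote draw at or near home | Must be day one | No |
| On site, blood completion only | Day one | No |
| On site, CK drawn first, NSAA afterwards | Day two | Yes |

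Only the third row satisfies both. It is permitted, but it does not fit footnote b's account of the day as a follow-up to complete blood collection, and it sits awkwardly with footnote q's request for early motor testing.

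**2. Biopsy.** It follows the functional tests and may be done on the day of Visit 19 or later. CK after biopsy is therefore possible. It concerns about 15 participants, at most 33, plus siblings. Against about 99 in the Full Analysis Set, that is roughly 15/99 = 15% to 33/99 = 33%. Siblings do not enter the secondary analyses (section 5.4).

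**3. Where else it occurs.** Section 1.3.2, footnote c, puts CK on the second day of Visit 31, while footnote n names Visit 31 in its own CK-first instruction. The Italy schedule (section 10.9.1.1, footnotes b and l) repeats the Year 1 conflict.

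**4. Size under assumed rises.** Let f be the ratio of post-test to pre-test CK. Take f = 1.1 and f = 1.5 as assumptions.

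- Within-arm shift in log change, if Baseline is pre-test and Week 52 post-test: ln f. ln 1.1 = +0.095; ln 1.5 = +0.405.
- Randomised contrast with the same f and the same share of post-test draws in both arms: ln f − ln f = 0.
- Randomised contrast if the post-test share differs by 10 points between arms: 0.10 × ln f = 0.010 to 0.041, about 1% to 4% on the ratio scale.
- Added between-boy variance if a share p is post-test: p(1 − p)(ln f)². At p = 0.5 this is 0.25 × 0.095² = 0.002 to 0.25 × 0.405² = 0.041. The documents give no standard deviation for log CK to set this against.

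**5. Cohort 2.** Section 3.1 includes, as exploratory, the CK change from the pre-treatment baseline to Year 2 Week 52 (Visit 35). The section 1.3.2 schedule shows no CK at Visit 20, so Visit 19 is the last scheduled value before Day 390, unless a dosing pause triggers the unplanned visits of section 5.3.2. Visit 35 is not split, and footnote n asks for CK before testing there. With a post-test Visit 19 value and a pre-test Visit 35 value, the ratio is multiplied by 1/f: 1/1.1 = 0.91 or 1/1.5 = 0.67. That is an apparent fall of 9% to 33% with no true change, and no concurrent control removes it.

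**The case against.** The best defence is that nothing is contradicted outright. Footnote b allocates blood samples only, and no passage assigns the NSAA to either day. Remote collection is optional, and a site can bring the boy back, draw CK and then test him. Footnote l is qualified by whenever possible, and footnote b gives a practical reason for the split. Both l and q send the ordering of assessments to the Functional Assessment Manual, which is not at hand and may settle the day. CK lies outside the alpha-controlled sequence, the primary endpoint is untouched, and both arms follow one schedule under blinding.

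Much of this stands, and it rules out several stronger readings that a reader might infer:

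- That the protocol schedules every Week 52 CK after functional testing. It does not; the order follows only when the second day is remote or confined to blood.
- That CK first is an absolute requirement. It is an instruction with a qualifier.
- That Baseline CK is known to be pre-test. It can be, but the same qualifier applies there.
- That CK will be drawn after biopsy. This is possible, in the subset only.
- That the treatment contrast is biased by a material percentage. That needs the draw order, the CK response or the biopsy share to differ by arm, and the documents give no basis for assuming any such difference.

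The qualifier does not dispose of the point. It covers circumstances that prevent the preferred order. Here footnote b itself prevents that order whenever a site uses the remote option that it offers.

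**Conclusion.** The point holds as an internal conflict in the schedule. A site that follows footnote b in its most natural form cannot follow footnote l at Visits 14 and 19, and Visit 19 is the endpoint visit for a secondary endpoint.

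The consequence is limited. For the randomised Week 52 comparison, the likely effects are a shifted within-arm change and added variance; a rise common to both arms cancels. The uncontrolled Cohort 2 change is more exposed, because there the rise does not cancel and would make CK appear to fall further than it did. That conclusion assumes that the Cohort 2 baseline is the last CK before dosing, which is the rule section 9.4.1 gives for Year 1, and that Visit 35 is sampled before testing.

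All sizes rest on the assumed 10% to 50% rise and on the direction of a rise after exertion. The documents support the concern through footnote l's rationale but give no magnitude.

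**What to change.** Reconcile footnotes b and l of section 1.3.1, footnotes c and n of section 1.3.2, and the Italy schedule, in one of two ways:

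1. Move CK to the first-day draw, before the NSAA and any biopsy, and move a sample that is not time-critical to day two. The documents give neither a CK tube volume nor the daily limit, so the central laboratory must confirm that the swap fits.
2. Keep CK on day two and state that functional tests and biopsy follow that draw. This needs an on-site second day and gives up the remote option.

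Under either choice, record the date and time of the CK draw, the NSAA and any biopsy.

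For values already collected, classify each CK as pre-test or post-test and add a sensitivity analysis that accounts for that status, for example as a covariate. Excluding all post-test values is not advisable, because it could leave few Week 52 observations. A change made midway also mixes draw conditions within Week 52, which is another reason to model draw status. Report the Cohort 2 change with the draw status of its Visit 19 baseline.

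The cost is a footnote and laboratory-manual edit, a few timing fields and one added analysis.

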1.3.2. Schedule of Activities – Year 2 and Long Term Follow Up

Period	Year 2																				Long-term follow up		Early Discontinuation Visit		
Visit Number/Description	Visit 20 ^{a,bb,cc}	Visit 21 ^{bb,cc}	Visit 22 ^{bb,cc}	Visit 23 ^{bb,cc}	Visit 24 ^{bb,cc}	Visit 25 ^{bb,cc}	Visit 26 ^{bb,cc}	Visit 27 ^{bb,cc}	Visit 28 ^{bb,cc}	Visit 29 ^{bb,cc}	Visit 29.2 ^b	Visit 30 ^{bb,cc}	Visit 30.1 ^{bb,cc}	Visit 30.2 ^{b,bb,cc}	Visit 31 ^{cc,cc}	Visit 31.2 ^{cc,cc}	Visit 32 ^{cc,cc}	Visit 33 ^{cc,cc}	Visit 34 ^{cc,cc}	Visit 35 ^{cc,cc}	Visits 36, 38, 40, 42 ^d	Visits 37, 39, 41, 43 ^d			
Visit Day	390	391	393	395	396	397& 398	399	403	410	417	423	431	437	449	463	479	509	629	749	930, 1290, 1470, 1650, 2010 ^d , 2190 ^d	Years 3, 4, 5, 6 ^d	Years 3, 4, 5, 6 ^d			
Visit Window (\pm days)	3 ^f	2 ^f	2 ^f	2 ^f	2 ^f	2 ^f	2 ^f	3 ^f	3 ^f	3 ^f	3 ^f	3 ^f	3 ^f	3 ^f	3 ^f	3 ^f	3 ^f	7 ^f	7 ^f	7 ^f	30 ^f	30 ^f			
Eligibility for Year 2 IP administration ^f	X																								
Hospital stay ^{dd}	X	→	→	→	→	X																			
Physical examination ^g	X	X	X		X		X	X			X				X			X	X	X	X	X	X		
Neurological examination ^g		X		X		X	X			X					X			X	X	X	X	X	X		
Height and Weight												X							X	X	X	X	X	X	
Vital signs (supine BP, respiration, PR, body temp, and O ₂ saturation) ^{h,i}	X	X	X		X		X	X			X				X			X	X	X	X	X	X		
12-Lead ECG ^j	X				X		X												X			X	X		
CBCL																			X	X	X	X	X ^e		
Laboratory Assessments ^k																									
Blood Samples																									
NAb to AAV9														X							X		X	X ^e	
ADA to mini-dystrophin and AAV9														X ^z	X ^z	X ^z	X				X	X		X	X ^e
ELISpot to mini-dystrophin and AAV9	X																		X					X ^w	X ^e
Viral Vector Shedding ^u								X									X		X	X	X			X	X ^e
Clinical safety (hematology, other) ^k		X	X					X	X		X				X		X	X	X	X	X	X	X	X ^e	

PFIZER CONFIDENTIAL

CT02-GSOP Clinical Protocol Template Phase 1 2 3 4 (04 September 2018)

Page 36

Period	Year 2																				Long-term follow up		Early Discontinuation Visit
	Visit 20 ^{a,bb,cc}	Visit 21 ^{bb,cc}	Visit 22 ^{bb,cc}	Visit 23 ^{bb,cc}	Visit 24 ^{bb,cc}	Visit 25 ^{bb,cc}	Visit 26 ^{bb,cc}	Visit 27 ^{bb,cc}	Visit 28 ^{bb,cc}	Visit 29 ^{bb,cc}	Visit 29.2 ^{b,cc}	Visit 30 ^{bb,cc}	Visit 30.1 ^{bb,cc}	Visit 30.2 ^{bb,cc}	Visit 31 ^{cc}	Visit 31.2 ^{bb,cc}	Visit 32 ^{bb,cc}	Visit 33	Visit 34	Visit 35	Visits 36, 37, 38, 40, 42 ^d	Visits 37, 39, 41, 43 ^d	
Visit Number/Description	Year 2, Week 1, Day 1	Year 2, Week 1, Day 2	Year 2, Week 1, Day 4	Year 2, Week 1, Day 6	Year 2, Week 1, Day 7	Year 2, Week 2, Days 8 & 9	Year 2, Week 2, Day 10	Year 2, Week 2, Day 14	Year 2, Week 3	Year 2, Week 4	Year 2, Week 5	Year 2, Week 6	Year 2, Week 7	Year 2, Week 9	Year 2, Week 11	Year 2, Week 13	Year 2, Week 18	Year 2, Week 35	Year 2, Week 52	Years 3, 4, 5, 6 ^d	Years 3, 4, 5, 6 ^d	Approved On: 28-Dec-2023 17:35 (GMT)	
Visit Day	390	391	393	395	396	397& 398	399	403	410	417	423	431	437	449	463	479	509	629	749	930, 1290, 1650, 2010 ^d	1110, 1470, 1830, 2190 ^d		
Visit Window (\pm days)	3 ^f	2 ^f	2 ^f	2 ^f	2 ^f	2 ^f	2 ^f	3 ^f	3 ^f	3 ^f	3 ^f	3 ^f	3 ^f	3 ^f	3 ^f	3 ^f	7 ^f	7 ^f	7 ^f	30 ^f	30 ^f		
Chemistry and hepatic safety ^k		X	X					X	X	X ^y	X			X	X	X	X	X	X	X	X	X	
Post IP intensified safety monitoring ^{k,s}		X	X					X	X		X												
Local and central laboratory testing ^x	X	X	X	X	X	X	X	X ^{gg}	X ^{gg}	X ^{gg}	X ^{gg}	X ^{gg}	X ^{gg}	X ^{gg}	X ^{gg}	X ^{gg}	X ^{gg}	X ^{gg}	X ^{gg}	X ^{gg}			
Cardiac Troponin I									X	X	X	X	X	X	X	X	X	X	X	X	X	X	
Biomarker (creatinine kinase) ^k			X					X	X	X	X			X	X	X	X	X	X	X	X	X	
Banked biospecimens for biomarkers ^l																				X	X		
Urine Samples																							
Clinical safety (urinalysis) ^k	X	X	X					X	X		X			X			X	X	X		X	X ^e	
Banked biospecimens for biomarkers ^l																				X	X		
Viral Vector Shedding ^u					X				X					X		X	X	X	X		X	X ^e	
Saliva Samples																							
Viral Vector Shedding ^u						X				X				X		X	X	X	X		X	X ^e	
Tissue Sample																							
Muscle Biopsy																						X ^{ff}	
Imaging Assessments																							
Echocardiogram ^m																				X		X	X ^e
Cardiac MRI ^{aa}																				X ^{aa}			

Period	Year 2																				Long-term follow up		Early Discontinuation Visit	
	Visit 20 ^{a,bb,cc}	Visit 21 ^{bb,cc}	Visit 22 ^{bb,cc}	Visit 23 ^{bb,cc}	Visit 24 ^{bb,cc}	Visit 25 ^{bb,cc}	Visit 26 ^{bb,cc}	Visit 27 ^{bb,cc}	Visit 28 ^{bb,cc}	Visit 29 ^{bb,cc}	Visit 29.2 ^{b,cc}	Visit 30 ^{bb,cc}	Visit 30.1 ^{bb,cc}	Visit 30.2 ^{bb,cc}	Visit 31 ^{cc}	Visit 31.2 ^{bb,cc}	Visit 32 ^{bb,cc}	Visit 33	Visit 34	Visit 35	Visits 36, 37, 38, 40, 42 ^d	Visits 39, 41, 43 ^d		
Visit Number/Description	Year 2, Week 1, Day 1	Year 2, Week 1, Day 2	Year 2, Week 1, Day 4	Year 2, Week 1, Day 6	Year 2, Week 1, Day 7	Year 2, Week 2, Days 8 & 9	Year 2, Week 2, Day 10	Year 2, Week 2, Day 14	Year 2, Week 3	Year 2, Week 4	Year 2, Week 5	Year 2, Week 6	Year 2, Week 7	Year 2, Week 9	Year 2, Week 11	Year 2, Week 13	Year 2, Week 18	Year 2, Week 35	Year 2, Week 52	Years 3, 4, 5, 6 ^d	Years 3, 4, 5, 6 ^d	Approved On: 28-Dec-2023 17:35 (GMT)		
Visit Day	390	391	393	395	396	397& 398	399	403	410	417	423	431	437	449	463	479	509	629	749	930, 1290, 1650, 2010 ^d	1110, 1470, 1830, 2190 ^d			
Visit Window (\pm days)	3 ^f	2 ^f	2 ^f	2 ^f	2 ^f	2 ^f	2 ^f	3 ^f	3 ^f	3 ^f	3 ^f	3 ^f	3 ^f	3 ^f	3 ^f	3 ^f	3 ^f	7 ^f	7 ^f	7 ^f	30 ^f	30 ^f		
Functional Assessments																								
FVC ^{n,t}																						X		X X ^e
NSAA ⁿ																					X	X	X X	X X
Ankle range of motion																					X	X	X X	X X
Ambulatory status																					X	X	X X	X X
Actigraphy ^o																					X	X	X X	X X
Clinical Outcome Assessments																								
Caregiver-completed																					X	X	X X	X X
Modified PODCI – Pediatric Parent ^p																					X		X X	
EQ-5D-Y Proxy ^p																					X		X X	
EQ-5D-5L																					X		X X	
PGIS:CG ^p																	X		X	X	X	X X	X X	
Participant-completed																								
Modified PODCI – Adolescent ^p																					X	X	X X	
EQ-5D-Y ^p																				X		X X		
PGIS ^p																				X		X X		
Clinical evaluator-completed																								
CGIS ⁿ																	X		X	X	X	X X	X X	
Health economic questionnaires																					X		X X	
HRU:CG																					X		X X	
WPAI:DMD Caregiver																				X		X X		

PFIZER CONFIDENTIAL

CT02-GSOP Clinical Protocol Template Phase 1 2 3 4 (04 September 2018)

Period	Year 2																				Long-term follow up		Early Discontinuation Visit ^e		
	Visit 20 ^{a,bb,cc}	Visit 21 ^{bb,cc}	Visit 22 ^{bb,cc}	Visit 23 ^{bb,cc}	Visit 24 ^{bb,cc}	Visit 25 ^{bb,cc}	Visit 26 ^{bb,cc}	Visit 27 ^{bb,cc}	Visit 28 ^{bb,cc}	Visit 29 ^{bb,cc}	Visit 29.2 ^{b,cc}	Visit 30 ^{bb,cc}	Visit 30.1 ^{bb,cc}	Visit 30.2 ^{bb,cc}	Visit 31 ^{c,cc}	Visit 31.2 ^{bb,cc}	Visit 32 ^{bb,cc}	Visit 33	Visit 34	Visit 35	Visits 36, 37, 38, 39, 40, 41, 42 ^d	Visits 37, 38, 39, 40, 41, 42 ^d			
Visit Number/Description	Year 2, Week 1, Day 1	Year 2, Week 1, Day 2	Year 2, Week 1, Day 4	Year 2, Week 1, Day 6	Year 2, Week 1, Day 7	Year 2, Days 8 & 9	Year 2, Day 10	Year 2, Day 14	Year 2, Week 3	Year 2, Week 4	Year 2, Week 5	Year 2, Week 6	Year 2, Week 7	Year 2, Week 9	Year 2, Week 11	Year 2, Week 13	Year 2, Week 18	Year 2, Week 35	Year 2, Week 52	Years 3, 4, 5, 6 ^d	Years 3, 4, 5, 6 ^d				
Visit Day	390	391	393	395	396	397& 398	399	403	410	417	423	431	437	449	463	479	509	629	749	930, 1290, 1650, 2010 ^d	1110, 1470, 1830, 2190 ^d				
Visit Window (\pm days)	3 ^f	2 ^f	2 ^f	2 ^f	2 ^f	2 ^f	2 ^f	2 ^f	3 ^f	3 ^f	3 ^f	3 ^f	3 ^f	3 ^f	3 ^f	3 ^f	3 ^f	3 ^f	7 ^f	7 ^f	7 ^f	30 ^f	30 ^f		
Study Interventions																									
Protocol-mandated glucocorticoid regimen ^q	X	X	→	→	→	→	→	→	→	→	→	→	→	→	→	→	→	→	→	X					
Background glucocorticoid regimen																				X	→	→	→	X ^v	X ^v
IP administration	X																								
Ongoing monitoring																									
Concomitant medications	→	→	→	→	→	→	→	→	→	→	→	→	→	→	→	→	→	→	→	→	→	→	→	X	
Serious and nonserious adverse event monitoring	→	→	→	→	→	→	→	→	→	→	→	→	→	→	→	→	→	→	→	→	→	→	→	X	

Abbreviations/Acronyms: →=continuous monitoring/event; AAV9= adeno associated virus serotype 9; ADA=anti-drug antibody; BP=Blood pressure; CG=Caregiver; CGIS=Clinician Global Impression of Severity; CBCL=Child Behavior Check List; ECG = electrocardiogram; ELISpot= Enzyme-Linked ImmunoSpot; EQ-5D-Y= EuroQol 5 Dimensions–Youth; FVC= Forced Vital Capacity; IP=investigational product; NAb=neutralizing antibodies; NSAA=North Star Ambulatory Assessment; PGIS= patient global impression of severity; PODCI=Pediatric Outcomes Data Collection Instrument; PR=pulse rate; temp=temperature.

a. Visit 20 – Year 2, Week 1, Day 1

- Prior to IP administration, the Investigator must confirm applicable Year 2 IP administration eligibility criteria (Section 7.1);
- Participants are to be admitted to the site;
- Participants will be instructed not to take their background glucocorticoid dose on Day 390 (Visit 20);
- The following assessments must be performed **prior to IP administration**: Physical examination, blood collection (ELISpot to mini-dystrophin and AAV9), urine sample collection, ECG and vital signs;

Period	Year 2																				Long-term follow up	Early Discontinuation Visit
	Visit 20 ^{a,bb,cc}	Visit 21 ^{bb,cc}	Visit 22 ^{bb,cc}	Visit 23 ^{bb,cc}	Visit 24 ^{bb,cc}	Visit 25 ^{bb,cc}	Visit 26 ^{bb,cc}	Visit 27 ^{bb,cc}	Visit 28 ^{bb,cc}	Visit 29 ^{bb,cc}	Visit 29.2 ^b	Visit 30 ^{bb,cc}	Visit 30.1 ^{bb,cc}	Visit 30.2 ^{b,bb,cc}	Visit 31 ^{c,cc}	Visit 31.2 ^{bb,cc}	Visit 32 ^{bb,cc}	Visit 33	Visit 34	Visit 35		
Visit Number/Description	Visit 20 ^{a,bb,cc}	Visit 21 ^{bb,cc}	Visit 22 ^{bb,cc}	Visit 23 ^{bb,cc}	Visit 24 ^{bb,cc}	Visit 25 ^{bb,cc}	Visit 26 ^{bb,cc}	Visit 27 ^{bb,cc}	Visit 28 ^{bb,cc}	Visit 29 ^{bb,cc}	Visit 29.2 ^b	Visit 30 ^{bb,cc}	Visit 30.1 ^{bb,cc}	Visit 30.2 ^{b,bb,cc}	Visit 31 ^{c,cc}	Visit 31.2 ^{bb,cc}	Visit 32 ^{bb,cc}	Visit 33	Visit 34	Visit 35	Visits 36, 37, 38, 40, 42 ^d	Visits 37, 39, 41, 43 ^d
Year 2, Week 1, Day 1	Year 2, Week 1, Day 1	Year 2, Week 1, Day 2	Year 2, Week 1, Day 4	Year 2, Week 1, Day 6	Year 2, Week 1, Day 7	Year 2, Week 2, Days 8 & 9	Year 2, Week 2, Day 10	Year 2, Week 2, Day 14	Year 2, Week 3	Year 2, Week 4	Year 2, Week 5	Year 2, Week 6	Year 2, Week 7	Year 2, Week 9	Year 2, Week 11	Year 2, Week 13	Year 2, Week 18	Year 2, Week 35	Year 2, Week 52	Years 3, 4, 5, 6 ^d	Years 3, 4, 5, 6 ^d	
Visit Day	390	391	393	395	396	397& 398	399	403	410	417	423	431	437	449	463	479	509	629	749	930, 1290, 1650, 2010 ^d	1110, 1470, 1830, 2190 ^d	
Visit Window (\pm days)	3 ^f	2 ^f	2 ^f	2 ^f	2 ^f	2 ^f	2 ^f	3 ^f	3 ^f	3 ^f	3 ^f	3 ^f	3 ^f	3 ^f	3 ^f	3 ^f	3 ^f	7 ^f	7 ^f	7 ^f	30 ^f	30 ^f

- Participants will receive an intravenous infusion of 2 mg/kg of methylprednisolone approximately **1 to 4 hours prior to infusion of IP**;
- IP administration over approximately 2 to 4 hours (-15 minutes or +30 minutes including flush);
- Vital signs will be monitored at approximately 30 minutes, 1, 2, 4, 8, and 10 hours after start of infusion, and 3 times per day after that for the duration of the hospital stay. Participants will remain as inpatients for at least 7 days after the infusion has terminated and will be discharged on Day 397, or later if deemed necessary by the Investigator (see [Section 8.2.10](#)).
- If adverse events (AEs) possibly related to IP administration are observed, participants should not be discharged until the events have resolved. Upon discharge, participants should stay near the site for at least 7 additional days to enable prompt follow-up in the event of any emergent AEs through Day 403 (Visit 28), or longer if deemed necessary.
